based on a multi-dimensional conceptual model of trust and measures trust in physicians and other health care providers [128-130]. Compared with previous scales, it showed improved internal consistency and variability [129, 131-132, 261]. Trust is measured by the sum of the 10 item scores, ranging from 10 to 50, with a higher score indicating higher trust [129, 131-132, 261]. As part of Specific Aim 3, the following outcomes will be measured for both intervention group and the usual care control group after initiation of treatment. Treatment choice: We will obtain data on primary and secondary treatments received, such as active surveillance, RP, RALP, EBRT, BT or PT via self report and verified from medical chart review. Satisfaction with Decision (SWD): The SWD scale measures satisfaction with healthcare decisions. It was developed in the context of postmenopausal hormone-replacement therapy decisions. The six-item scale has excellent reliability (Cronbachs alpha = 0.88) [262]. Regret scale: Regret represents the unsettling feeling of having made a poor choice of treatment, persistent doubt, and a wish to change one's mind. The Regret scale is defined by three items that assess (1) the mans wish that he could change his mind about the kind of treatment he has received, (2) his feeling that he would be better if he had chosen the other treatment, and (3) whether he is bothered by the fact that other men received very different treatments for their PCa [33]. This scale exhibited good psychometric properties and has been extensively studied [33, 174, 263-265]. Following objective and subjective outcome measures will be assessed at baseline and at each post-treatment follow-up period (3,6,12 and 24 months) for intervention group and usual care control group. Biochemical recurrence: We will define progression of PCa as a change in PCa stage to an advanced stage or PSADT, post treatment [11, 44-45, 55, 160, 203]. We will obtain PSA data at baseline, prior to treatment, and post treatment at three months interval for 18 months. A PSA value of greater than 0.2 ng/ml indicates disease recurrence for surgery patients. For radiation therapy patients, we will adopt the Houston / Phoenix definition of the current PSA nadir + 2 ng/mL, with date of failure determined at call as the biochemical recurrence after radiation therapy [11, 44-45, 55, 160, 203]. Any treatment within six-month of diagnosis will be considered as adjuvant (review by investigators Drs. [name], [name], and [name]). D.2.4.3.2 Medical complications: We will identify complications that occur during either index or subsequent hospital admissions within 30 days of treatment [266]. Alibhai, et al. (2005), has grouped complications after RP into seven mutually exclusive categories: cardiac; respiratory; genitourinary; wound or bleeding; vascular; miscellaneous medical; and miscellaneous surgical [266]. Similarly, a list of complications for each treatment type will be developed by literature review and the physician investigators and consultants. Generic HRQoL- Medical Outcome Study Short Form: HRQoL data will be obtained using the Medical Outcome Study Short Form (SF-36) a multi-item scale that assesses eight health domains. This instrument can be self-administered or administered by a trained interviewer, either in person or by telephone. It has been tested extensively for reliability ($r=0.80 - 0.93$) and validity (Cronbachs $=0.92$). Scores on each sub-scale range from 0 to 100, with higher scores indicating better HRQoL [267-271]. Prostate Cancer HRQoL- Expanded Prostate Cancer Index (EPIC): The EPIC was developed for comprehensive assessment of HRQoL in men with PCa. It is a 50-item expanded edition of the 20-item UCLA Prostate Cancer Index (PCI) and complements other instruments by measuring a broad spectrum of urinary, bowel, sexual and hormonal symptoms. It has good psychometric properties: test-retest reliability and internal consistency are high for EPIC and for most of the subscales [189, 272-273]; construct validity was established using SF-36 as a generic core measure and a cancer-related HRQoL instrument, the Cancer Rehabilitation System-Short Form [189, 272-273]; and is easy to understand and complete [192]. American Urological Association Symptom Index (AUA-SI): The AUA-SI, a clinically sensible, reliable, valid and responsive index widely used for clinical and research purposes [274], has good internal consistency (Cronbachs $=0.86$), excellent test-retest reliability ($r=0.92$) and sensitivity to change with preoperative scores decreasing from a mean of 17.6 to 7.1 by four weeks after prostatectomy ($p<0.001$). D.2.4.3.6 Patient Satisfaction Questionnaire (PSQ-18): This 18-item survey [a shorter version of the original Patients Satisfaction Questionnaire [275], assesses global satisfaction with medical care and satisfaction with six aspects of care: technical quality; interpersonal manner; communication; financial aspects of care; time spent with doctor; and accessibility of care. It has demonstrated good internal consistency (Cronbachs $=0.86$) and excellent test-retest reliability ($r=0.92$). Memorial Anxiety Scale for Prostate Cancer (MAX-PC): The 18-item MAX-PC identifies three aspects of PCa-related anxiety. It has high internal consistency and concurrent and discriminant validity[276]. The Center for Epidemiologic Studies Depression (CES-D) scale: This 20-item, self-report scale to identify depression in the general population covers major components of depression, with an emphasis on affective components: depressed mood; feelings of guilt and worthlessness; feelings of helplessness and hopelessness; psychomotor retardation; loss of appetite; and sleep disorder [277]. Potential confounding variables: Disease severity: We will adjust for disease severity using information on PCa stage or TNM stage, grade and histology from electronic medical records. Gleason score: The Gleason score is a sum of the predominant pattern and the second most

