obtaining consent from patients urologist/physician; 3) confirming eligibility; 4) screening via phone and interview to assess willingness to participate; 5) obtaining informed consent and HIPAA permissions; 6) baseline assessments; and 7) follow-up assessments. The study and consent form comply with HIPAA Standards for Privacy of Individually Identifiable Health Information. The draft study design and protocol have been approved by the University of Pennsylvania IRB. Future changes will be reviewed and approved prior to implementation. Participant availability: UPHS is a large hospital and physician network in greater Philadelphia area. Approximately 1,600 patients with newly diagnosed PCa are evaluated annually: 40-50% undergo surgery (RP or RALP); 30-40% undergo EBRT or BT; 10-20% undergo PT. The urology clinic at the Hospital of the University of Pennsylvania (HUP) treats more than 60% of this group; the rest are treated at Presbyterian Medical Center and Pennsylvania Hospital. Additionally, UPHS has a proton therapy center, providing a unique opportunity to study this new technology. The Philadelphia Veterans Administration Medical Center (PVAMC) cares for 33,000 veterans in Philadelphia area and evaluates ~400 patients with newly diagnosed PCa each year. Fox Chase Cancer Center evaluates ~500 patients with newly diagnosed PCa each year. Together, UPHS, PVAMC, and Fox Chase Cancer Center provide care to socio-demographically diverse population of ~2,500 men newly diagnosed with PCa each year. Thus, our study sample requirement of 720 patients (33% of the available pool) can be fulfilled comfortably, as demonstrated by the successful recruitment for our earlier studies. Recruitment: Prior to study initiation, investigators will explain the study objectives to physicians who actively treat PCa at the UPHS, PVAMC, Fox Chase urology clinics. During a patient's initial visit, Drs. [name], [name], or [name] will briefly introduce the study to the patient. Each week, the research assistant will contact the participating physician offices to obtain contact information for those patients who have expressed an interest in the study. Potential participants will be contacted during their office visits, at which time those eligible may agree to participate and provide informed consent, request additional information and/or time to think or request to be contacted later. Patients who request to be contacted later will be sent study information, a consent form and a prepaid return envelope. Participants will discuss the consent form with research assistant prior to signing, at which time all questions will be answered. During enrollment, compensation of \$20 will be provided. Using a similar recruitment strategy in our prior PCa studies, we had achieved enrollment and retention rates of 85% or higher. The expected number of 60 participants in each treatment group (AS, RP, RALP, EBRT, BT or PT) will be achieved as follows: (1) each recruited participant randomly assigned to the conjoint analysis intervention group will meet with research assistant to complete the computer-based conjoint analysis tasks and other surveys before initiation of treatment or making a treatment decision; (2) after treatment decision is made, patients (both cases and controls) will be assigned to the appropriate group based on treatment; (3) this process will continue until we reach the required number of participants in each group. To achieve this, we may evaluate and obtain baseline data including conjoint tasks from patients in excess of the required 360 participant each in the intervention and control groups. Based on our prior prospective cohort studies, to fulfill sample requirement of 60 participant in each treatment group ($60 \times 2 \times 6 = 720$), allowing for attrition we expect to obtain baseline assessment including conjoint tasks for 800 participants (10% excess). The cohort that doesn't get assigned for further follow-up due to targeted group enrollment accrual will be analyzed to ensure comparability. D.2.2 Process of stratified randomization: We will recruit 720 participants stratified by three hospitals-UPHS, PVAMC, or Fox Chase Cancer Center (Figure 3). [name] will create randomization sequences for each hospital using a pseudo-random number generator with random blocking and will place the treatment assignments in sealed, opaque envelopes. All investigators, staff and referring physicians will be masked to the treatment assignment, except the research assistant who will open the envelope and notify participants of group assignment. Participants will be instructed not to reveal their group status to physicians or study personnel, except in case of emergency or if necessary for medical reason, which we believe to be unlikely.

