After obtaining informed consent, baseline data will be obtained in person prior to the initiation of treatment. Participants will meet with the research assistant to complete the computer-based conjoint analysis tasks. Patient identifiers will be removed to maintain data confidentiality. Only the PI will have access to the master files. For conjoint analysis, each participant will be asked to express his preference for attributes and attribute levels for active surveillance and five active treatments for clinically localized PCa (RP, RALP, EBRT, PT, BT) based on choice sets presented. The choices will vary based on the differing attributes of various treatments ascertained in prior work and focus groups. After pilot testing and refining the conjoint task in Phase 1, final attributes and levels will be used. Trade-offs among treatment features will be calculated in patient-specific utilities or part-worths associated with the attribute levels in the study. For other outcomes, participants will receive the following surveys via mail within 1-2 weeks after enrollment and prior to treatment initiation: SF-36, EPIC, AUA-SI, regret scale, CES-D, MAX-PC, SWD, PSQ-18, CPS, DCS and trust scale. Demographics, health and family history, clinical covariates and cancer progression data will be collected at 3, 6, 12 and 24 month follow-up. Histological tumor grade Gleason score and PSA and annual Elixhauser comorbidity score [257-258] will be obtained from the Pennsylvania Integrated Clinical and Research Database (PICARD), a UPHS, Fox-Chase Cancer Center electronic database, and PVAMC administrative and patient HER database. Retention and survey administration: During enrollment, importance of active participation will be emphasized. All participants will complete self-administered surveys at baseline within 1-2 weeks after enrollment (prior to treatment initiation) and again 3,6,12 and 24 months post-enrollment (see Appendix for copies of instruments, consent and medical chart review form). Non-respondents will be contacted via telephone after 10 days. In case of non-response due to death, cause of death will be noted and the physician investigators will determine cause of death (PCa or non-PCa related). The PCa conjoint analysis task, DCS, CPS and trust scale will be administered at baseline only, immediately after diagnosis of PCa and before treatment decision. Procedure for Data Sharing and Modification coordination: In Phase-1 on the study, data will be generated from focus group meetings that will take place on Penn campus. Focus group data will not be shared with other sites. This data will be used to generate a conjoint analysis instrument. This conjoint analysis instrument will be administered to participants in the intervention arm at all three sites during the Phase-2 of the study. The paper copies of various instruments that all participants complete will be stored at Penn campus in a secure office. In addition, clinical data obtained through chart abstraction will also be stored at Penn campus in a secure office. All electronic data bases will be pass word protected and only the study personal will have access to this data. Raw data will not be shared with other sites, only results in aggregate format with de-identified information will be made available to other sites. Each site PI will be responsible for addressing modifications. Additionally, the Penn site PI [name] will have overall responsibility of tracking all modifications. In case of a reportable event at a site, the site PI will inform Penn IRB and Penn site PI regarding the reportable events. Additionally, during Phase-1 of the study, we will conduct audio/video recording of focus group meetings.

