patients in decision (measured using CPS) using multi-nominal regression model to adjust for observed covariates. Then we will examine if these associations vary across intervention and usual care control groups. We then will repeat the model with other independent variables (decision conflict and trust). Next, we will test the association denoted by path c (direct effect of DCS, CPS, and trust on outcomes). For continuous outcomes (HRQoL, AUA-SI, MAX-PC, CES-D, SWD, and PSQ-18), we will compute area under the curve (AUC) for each measure for each patient. We will analyze AUC summaries with univariate linear models. In our main analysis we will analyze the series of functional status measures using linear mixed models that predict the outcome from time, independent variables and their interaction. We will repeat the analyses described for path c, this time by including treatment received in the models. We will test if the observed effects of DCS, CPS or trust on outcomes will be weaker after controlling for treatment. These analyses will be performed within and between groups (intervention and usual care controls). Specific Aim 3: Hypothesis: Prostate cancer patients in the intervention group undergoing conjoint analysis-value clarification exhibit improved treatment choice, satisfaction with decision, lower regrets, and improved objective and subjective outcomes. Analysis for Specific Aim 3 uses intent-to-treat approach: all randomized participants will be included regardless of whether they drop out of the intervention or study. Analysis will involve comparison of the primary outcomes between intervention and usual care control groups. Improved treatment choice is operationalized as the likelihood of low-risk PCa patients receiving active surveillance than active treatment, and will be compared between intervention and usual care control group. To allow for different trajectories of the outcome measures and to afford flexibility in making contrasts within participants over time and across participants, while simultaneously controlling for potential confounders, we propose the participant-specific or mixed effects linear model, in which the mean outcome depends on fixed covariates and random effects. The primary fixed effects will be indicators for intervention group and hospital. We will also stratify the analysis by type of treatment. The random effects represent the unobserved factors that lead to variation of the individual participants outcome. Random intercepts for each participant permit modeling of natural variation across participants at baseline. In addition, random slopes or random effects for the trajectory of each participant over time, allow for variation of each participant about a mean, overall trajectory across all participants. Although less robust to model misspecification, the mixed effects paradigm offers special flexibility in longitudinal data when exposures vary over time and when dropout and missed visits lead to unbalanced groups. The target of inference is the participant-specific response to treatment over time. At each time point of interest, we will estimate from the fitted model the difference from baseline in outcome for the treatment and control groups and test the difference between these differences. Both univariate and multivariate results will be reported in terms of Wald test, point estimates, and 95% confidence intervals. Specific Aim 4: Hypothesis 4: Prostate cancer patients whose treatment is more concordant with their values markers will experience improved subjective and objective outcomes. This specific aim s for intervention group only. We will analyze the association of the concordance between stated individual preferences and actual treatment received with objective (PCa recurrence and complications), subjective (HRQoL, psychological wellbeing, SWD, and satisfaction with care) outcomes, across treatment groups, adjusting for covariates. Association between the value markers (profiles) and measures of outcomes and personal and clinical characteristics: The value markers will be studied for their relationship with socio-demographic and clinical characteristics. We will also assess the association of value markers with outcomes. We will perform logistic regression with outcomes as the dependent variable and dummy variables for the utility-based profiles obtained earlier as independent variables. We will perform this evaluation with and without adjusting for patient attributes in the logistic model. For each case (adjusting and not adjusting for patient attributes), the evaluation of association between these profiles and outcomes will be based on a likelihood ratio test of the set of odds ratios corresponding to the dummy variables of the profiles. Additionally, we will perform a sequence of pair wise tests of comparisons of the profiles in terms of the proportion of type of treatment received based on the Holms multiple comparisons approach. This procedure is hierarchical in that it will identify the utility-based profile at the start of the process before making other comparisons, thus protecting the Type I error from additional comparisons. Specifically, Holms approach tests each pair-wise comparison in ascending order of p-values. Successively larger p-values have less rigorous alpha. The sequential Holm tests terminate after the first non-significant comparison so no subsequent comparison is significance. Concordance and its assessment: Understanding and respect for the patients preference and values is the main aspect of concordance [69, 73]. Thus a first step in concordance involves the physician extracting and understanding the patients view, followed by an agreement between the physician and patient regarding a management plan that integrates their views. There exist many definitions of concordance. For the purpose of this study, we operationalized concordance as agreement between a patients value markers and the attributes (or characteristics) of the treatment that

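### The plan contradicts itself on who does the conjoint task and on whether the Aim 2 predictors precede the treatment decision; SWD, regret and Aim 3 baseline timing also need settling

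*Combined protocol and SAP*

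**What the plan says.** All references are to the combined protocol and SAP.

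- **Survey timing.** Study Procedures, repeated in D.2.3, first says: "After obtaining informed consent, baseline data will be obtained in person prior to the initiation of treatment". It then says: "For other outcomes, participants will receive the following surveys via mail within 1-2 weeks after enrollment and prior to treatment initiation". The listed set is "SF-36, EPIC, AUA-SI, regret scale, CES-D, MAX-PC, SWD, PSQ-18, CPS, DCS and trust scale".
- **DCS, CPS and trust.** Primary outcome variable(s) and D.2.4.1 describe their measurement as at baseline, right after the treatment decision and before treatment starts. D.2.3 and Study Procedures say that these three scales and the conjoint task are given only at baseline, after diagnosis and before the decision.
- **SWD and regret.** D.2.4.2 places both after treatment has started.
- **Conjoint task.** The Abstract contrasts a conjoint-task arm with usual care. D.2.2.2 describes usual care as educational material. The data-sharing text in Study Procedures assigns the instrument to the intervention arm. Subject recruitment and D.2.1.2 expect conjoint tasks from both groups, 800 men in all.
- **Randomisation.** The seven recruitment steps end "5) obtaining informed consent and HIPAA permissions; 6) baseline assessments; and 7) follow-up assessments", with no step for randomisation. D.2.2 masks investigators, staff and referring physicians, "except the research assistant who will open the envelope and notify participants of group assignment". Subject recruitment describes men "randomly assigned to the conjoint analysis intervention group will meet with research assistant to complete the computer-based conjoint analysis tasks and other surveys".
- **Analysis.** D.2.4.3 says that "outcome measures will be assessed at baseline and at each post-treatment follow-up period (3,6,12 and 24 months"). Aim 3 estimates "the difference from baseline in outcome for the treatment and control groups and test the difference between these differences".

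**The concern.** Four things are left open, in descending order of weight.

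1. **The contrast.** D.2.2.1 shares conjoint results with the intervention group only. If only that arm does the task, Aim 3 tests doing the task plus sharing the results. If both arms do it, Aim 3 tests sharing alone. Sites that follow different sentences would deliver different comparisons.
2. **The Aim 2 predictors.** Aim 2 models treatment received on CPS, then on DCS and trust. Scores taken after the decision may reflect the choice that they are meant to predict.
3. **SWD and regret.** One regret item asks about the treatment the man has already received. It cannot be answered before treatment starts.
4. **The Aim 3 baseline.** If knowing the arm or doing the task shifts a score before baseline is recorded, that shift enters the change-from-baseline contrast. The bias is toward zero if the early and later effects share a sign, and away from zero if they do not. MAX-PC, CES-D and PSQ-18 are more plausibly exposed than SF-36, EPIC or AUA-SI. Treatment choice, recurrence and complications are not exposed in this way, nor are DCS, CPS and trust, which D.2.3 gives at baseline only.

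**Working it through.** **Who does the task**

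| Reading | Where |
|---|---|
| Intervention arm only | Abstract; D.2.2.2; data-sharing text in Study Procedures; consistent with Aim 4, which is limited to that arm |
| Both groups, or 800 men | D.2.1.2; Subject recruitment |
| Open to either | The each-participant wording in Study Procedures and Specific Aim 1 |

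With equal allocation, an intervention-only task gives 800 / 2 = 400 men with conjoint data for Aim 1, against 800 if both arms do it.

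**DCS, CPS and trust.** The D.2.4.1 phrase can mean one time point (after the decision) or two (baseline, and again after the decision). Either reading conflicts with a single measurement before the decision in D.2.3.

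**SWD and regret.** The mailing is limited by treatment initiation, not by the decision. SWD could therefore be answered after the decision and before treatment, but D.2.4.2 does not say so. The Aim 2 area-under-the-curve (AUC) analysis includes SWD. The Aim 4 concordance analysis lists SWD among outcomes whose primary comparison is baseline against six and 24 months. Both need one stated timing.

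**Scale of the baseline issue.** Inputs from Accrual: 360 per arm, 10% loss, intra-class correlation 0.3, four follow-ups, SD 8 to 14 (given for PCI and SF-36 only), 80% power, two-sided 0.05. Compound symmetry is assumed. n = 360 × 0.9 = 324 per arm.

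*The plan's own figure.* The variance factor for a mean of four follow-ups is (1 + 3 × 0.3)/4 = 0.475. The detectable difference is 2.802 × 8 × √(2 × 0.475/324) = 1.21 points, matching the stated 1.2 at SD 8. This has no baseline term, so it is not the yardstick for Aim 3.

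*Change at one time point.* Variance = 2 × (1 − 0.3) = 1.4 SD². SE = √(1.4 × 2/324) = 0.0930 SD. Detectable difference = 2.802 × 0.0930 = 0.260 SD, which is 2.08 points at SD 8 and 3.65 at SD 14.

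*Bias from an early arm difference b with no later effect.*

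- Raw change or categorical time: the bias is −b.
- Linear time at 0, 3, 6, 12 and 24 months, complete data: mean time = 9 and Sxx = 81 + 36 + 9 + 9 + 225 = 360. Slope bias = −9b/360 = −0.025b per month. This is −0.075b, −0.15b, −0.30b and −0.60b at 3, 6, 12 and 24 months.
- Aim 3 does not state how time is coded.

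*False-positive rate* = P(|Z + bias/SE| > 1.96), before the Bonferroni correction in the Analysis Plan. For linear time with random intercepts, the slope SE = √(2 × 0.7/(324 × 360)) = 0.00346 SD per month, so bias/SE in absolute value is 0.025b/0.00346 at every time point.

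| Assumed b (SD) | Raw change, one time point | Linear time, random intercepts |
|---|---|---|
| 0.05 | 0.08 | 0.065 |
| 0.10 | 0.19 | 0.11 |
| 0.20 | 0.58 | 0.30 |

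Aim 3 also allows random slopes. Added slope variance widens the SE and lowers the last column.

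**The case against.** **On the baseline.** Figure 3, cited for the randomisation process, is not available and may give the order. The only ordered list puts baseline directly after consent. The surveys completed by men already assigned are not identified with the mailed set. In-person and mailed collection can coexist, since the mailing is for the other outcomes. All of this stands. A reader might infer that baseline is taken after the arm is known and that Aim 3 is therefore biased. The text permits that order but does not establish it.

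**On the error rates.** No document figure supports any value of b, and no SD is given for MAX-PC, CES-D or PSQ-18. The rates show sensitivity only. A reader might also take the mean of four follow-ups minus baseline, which gives a rate of 0.78 at b = 0.20 SD. Aim 3 tests each time point, so that is not its contrast.

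**On the task.** The one sentence assigning the instrument to an arm names the intervention arm, and the each-participant wording can mean each man who does the task. That narrows the conflict but does not remove it: the both-groups and 800-men wording remains. The profile power in Accrual uses allocations of 25 against 10 and 35 against 35, and 60 per group. Having 400 men instead of 800 is therefore no shortfall against the plan's own power basis.

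**On SWD.** It would be too strong to call every pre-treatment SWD score meaningless. The objection holds fully only for the regret item on treatment received.

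**Conclusion.** Should-fix, resting on the two written contradictions: who does the conjoint task, and whether DCS, CPS and trust precede the treatment decision. A missing figure could settle the order of randomisation, but it would not remove sentences that disagree with each other. The first contradiction decides what Aim 3 compares and whether Aim 1 has about 400 or 800 men. The second decides whether the Aim 2 scores can be read as predictors of treatment.

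The regret timing is a smaller contradiction of the same kind, and SWD needs one stated time. The Aim 3 baseline is an unsecured step of unknown consequence. The rates in the table depend on the assumed b, no later effect, compound symmetry at 0.3, complete data for 324 per arm, and no multiplicity correction.

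**What to change.** 1. Reconcile the Abstract, D.2.1.2, D.2.2.2, Study Procedures, Subject recruitment and Specific Aim 1 on who does the conjoint task. Make the 800 count match, and state whether Aim 3 tests the task plus sharing or sharing alone.
2. State that DCS, CPS and trust, where used as Aim 2 predictors, are taken before the treatment decision. Correct Primary outcome variable(s) and D.2.4.1.
3. Remove regret from the pre-treatment mailing. State one timing for SWD, and make the Aim 2 AUC analysis and the Aim 4 baseline comparison agree with it.
4. State that the SF-36, EPIC, AUA-SI, MAX-PC, CES-D and PSQ-18 baselines are completed after consent, and before the envelope is opened and any conjoint task, in both arms. The in-person visit in Study Procedures could serve.

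Items 1 to 3 are mainly wording. Item 4 lengthens the visit: EPIC, CES-D, MAX-PC and PSQ-18 total 50 + 20 + 18 + 18 = 106 items, with SF-36 and AUA-SI on top.
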